#### **5.4 Prohibited Medications/Treatments**

There are no medications/treatments that would prohibit participants from inclusion and continued assessment in this study.

Patients on the following medications will be counseled on possible interactions with memantine and particular caution will be taken with dose escalation and side effect monitoring: drugs that may increase the serum concentration of memantine (alkalinizing agents, bupropion, carbonic anhydrase inhibitors) and drugs that

may enhance the adverse/toxic effects of memantine (trimethoprim and other NMDA receptor antagonists). Supportive medications typically used during chemotherapy for breast cancer do not have drug-drug interactions with memantine.

### **5.5 Duration of Therapy**

Treatment will continue until 4 weeks (range 2-12 weeks) after the last dose of systemic chemotherapy or until:

- Unacceptable adverse event(s)
- Inter-current illness that prevents further administration of treatment, **OR**
- Participant decides to withdraw from the study

Decisions to remove a participant from the trial or discontinuation of treatment before planned study completion will be undertaken in conjunction with consultation from the study PI.

### **5.6 Duration of Follow Up**

For determination of study endpoints, participants will be followed until completion of the primary endpoint (approximately 4 weeks after chemotherapy completion). A subset of participants who volunteer for extended longitudinal follow-up will be reassessed for exploratory endpoints at 6-months post-chemotherapy. All participants (including those withdrawn from protocol therapy for AEs) will be followed after removal from study treatment as stipulated in the protocol, unless the participant decides to withdraw from the study.

### **5.7 Study Withdrawal**

Participants will be removed from protocol therapy and the PI notified when any of the criteria listed in section 5.5 apply. The reason for discontinuation of the protocol therapy will be documented on the eCRF.

If a participant decides to withdraw from the study (and not just from protocol therapy) an effort will be made to complete and report study assessments as thoroughly as possible. At the time of withdrawal, the PI will attempt to establish as completely as possible the reason for the study withdrawal.

- The patient will be asked if they are willing to allow for the abstraction of relevant information from their medical record in order to meet secondary objectives outlined in the protocol.
- The patient will be asked if they are willing to complete the Modified Brief Medication Questionnaire-Specific at the time of study withdrawal.
- If the reason for removal of a participant from the study is an adverse event, the principal specific event will be recorded on the eCRF.

## 5.8 Study Measures

Pre- and post-chemotherapy assessments will each take approximately 70 minutes to complete. An optional 10-minute break will be offered during the assessment to minimize fatigue.

### OBJECTIVE COGNITIVE FUNCTION MEASURES

#### 5.8.1 Delayed Matching to Sample Test (DMS)

The Delayed Matching to Sample Test (DMS) is a computerized cognitive assessment of visual working memory. The DMS will be administered using CANTAB eclipse software (Cambridge Cognition, Cambridge, UK). The participant is shown an image with four patterns and asked to match patterns simultaneously or after delay. We will use the percent correct at the 12-second delay on the DMS test for the primary analysis. The DMS will take 7 minutes to complete. All participants who are enrolled in the trial will be evaluated pre- and post-chemotherapy.

#### 5.8.2 Hopkins Verbal Learning Test-Revised (HVLT-R)

The HVLT-R is an objective measure of verbal learning and memory. The examiner reads a list of 12 nouns to the participant, who repeats as many words as remembered. Approximately 20-25 minutes later, participants are asked to recall as many words as possible. Then, the examiner reads a list of 24 words, including the 12 words from the original list, and the participant is asked to determine which words were and were not on the original list. These tasks result in three subscales: total recall, delayed recall, and delayed recognition. The HVLT-R will take 5 minutes to complete. All participants who are enrolled in the trial will be evaluated pre- and post-chemotherapy.

#### 5.8.3 Rapid Visual Information Processing (RVP)

The Rapid Visual Information Processing Test (RVP) is a computerized assessment of processing speed. The RVP will be administered using CANTAB eclipse software (Cambridge Cognition, Cambridge, UK). The participant is shown a series of pseudo-random digits from 2 to 9 and asked to recognize target digit sequences by pressing a button on the screen as quickly as possible. The RVP will take 7 minutes to complete. All participants who are enrolled in the trial will be evaluated pre- and post-chemotherapy.

#### 5.8.4 One Touch Stockings of Cambridge (OTS)

The One Touch Stockings of Cambridge Test (OTS) is a computerized assessment of executive function. The OTS will be administered using CANTAB eclipse software (Cambridge Cognition, Cambridge, UK). The participant is shown two displays with three colored balls presented as stacks suspended from a beam and a row of numbered boxes along the bottom of the screen. In the first set of problems, the participant is asked to move the balls in the lower display to match that of the upper display. In the next set, the participant is asked to work out in their head how many moves are required to reach the

solution to each problem. The OTS will take 10 minutes to complete. All participants who are enrolled in the trial will be evaluated pre- and post-chemotherapy.

#### **5.8.5 Digit Span**

The Digit Span is an objective measure of attention and working memory. The participant is asked to recite sequences of numbers in forward, backwards, and sequential order. The Digit Span will take 4 to 7 minutes to complete. All participants who are enrolled in the trial will be evaluated pre- and post-chemotherapy.

#### **5.8.6 Controlled Oral Word Association Test (COWA)**

The COWA is an objective measure of verbal fluency. The participant is asked to name as many words as she can, excluding proper nouns, in one minute. This is repeated for a total of three different letters. The COWA will take 4 minutes to complete. All participants who are enrolled in the trial will be evaluated pre- and post-chemotherapy.

#### **5.8.7 Animal Naming Test (ANT)**

The ANT is an objective measure of semantic fluency. The participant is asked to name as many animals as she can in one minute. All participants will be evaluated pre- and post-chemotherapy.

#### **5.8.8 Wechsler Adult Test of Reading (WTAR)**

The Wechsler Adult Test of Reading (WTAR) is an objective measure of intelligence quotient. The participant reads 50 irregularly spelled words to provide estimated premorbid intelligence. The WTAR will take 3 minutes to complete. All participants who are enrolled in the trial will be evaluated pre-chemotherapy only.

#### **5.8.9 Blessed Orientation Memory Concentration Test (BOMC)**

The BOMC is a six-item screening measure of cognitive function that assesses orientation, language, attention, concentration, and memory. It has good reliability and validity and has been incorporated into cancer-specific geriatric assessments. A score  $\geq 11$  has been used to suggest severe cognitive impairment. The BOMC will take less than 5 minutes to complete. All participants who are enrolled in the trial will be evaluated pre-chemotherapy.

### **SELF-REPORT COGNITIVE FUNCTION MEASURE**

#### **5.8.10 Modified Patient Reported Outcomes Measurement Information System – Cognitive Function (PROMIS-Cognitive Function)**

The National Institute of Health's Patient-Reported Outcomes Measurement Information System (PROMIS) contains a cognitive function bank. We will use the PROMIS Cognitive Function 8a short form. Scores for all PROMIS measures are reported on the T-score metric in which the mean=50 and standard deviation (SD) = 10 are centered on the general population means. Higher scores represent

greater degrees of cognitive complaints. We will add three items to assess self-perceived pre-cancer cognitive ability and one item to explicitly assess memory. The PROMIS Cognitive Function will take less than 5 minutes to complete. All participants who are enrolled in the trial will be evaluated pre- and post-chemotherapy.

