### **3.2 Secondary Endpoints**

**3.2.1** Changes in other objective (HVLT-R, RVP, OTS, Digit Span, COWA, Animal Naming Test) and self-reported (PROMIS Cognitive Function) cognitive measures will be measured from pre- to post-chemotherapy.

**3.2.2** Depression (PROMIS-Depression), Anxiety (PROMIS-Anxiety), fatigue (Functional Assessment of Chronic Illness Therapy – Fatigue, FACIT-F), menopausal status (Hormonal Status Questionnaire and follicle stimulating hormone level, FSH), and perceived cognitive effort (NASA-Task Load Index, NASA-TLX) will be measured pre- and post-chemotherapy. Baseline IQ (Wechsler Adult Test of Reading, WTAR) will be measured pre-chemotherapy only.

**3.2.3** Health-related quality of life (Functional Assessment of Cancer Therapy – General, FACT-G) and functional status (Patient-reported Karnofsky Performance Status, Patient-KPS) will be measured pre- and post-chemotherapy.

**3.2.4** Recruitment will be measured as proportion of approached participants who agree to enroll and number of participants enrolled per month. Retention will be measured as proportion of enrolled participants who complete the primary outcome measure pre- and post-chemotherapy. Adherence will be measured as patient-reported proportion of prescribed doses of memantine actually taken.

**3.2.5** Safety will be measured as the frequency of reported adverse events (AEs).

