### **3.3 Exploratory Endpoints**

**3.3.1** Changes in the DMS, HVLT-R, RVP, OTS, Digit Span, COWA, Animal Naming Test, and PROMIS Cognitive function will be measured from pre- to 6 months post-chemotherapy in a subset of participants who volunteer for extended longitudinal observation.

**3.3.2** Changes in PROMIS-Depression, PROMIS-Anxiety, FACIT-F, FACT-G, and Patient-KPS will be measured from pre- to 6 months post-chemotherapy in a subset of participants who volunteer for extended longitudinal observation.

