### **5.8.14 Patient Reported Outcomes Measurement Information System – Sleep Disturbance**

The National Institute of Health's Patient-Reported Outcomes Measurement Information System (PROMIS) contains sleep bank. We will use the PROMIS Sleep Disturbance Short Form. Higher scores represent greater sleep difficulties. The PROMIS Sleep Disturbance Short Form will take less than 2 minutes to complete. All participants who are enrolled in the trial will be evaluated pre- and post-chemotherapy.

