### 9.3 Data Analysis Plans

The primary outcome is change in the DMS score. A paired t-test will test if the change in DMS score from pre- to post-chemotherapy is statistically different from historical controls. Pre- to post-chemotherapy, as well as pre- to 6 months post-chemotherapy, changes in all other cognitive measures will also be evaluated using paired t-tests.

Linear regression models will be used to cross-sectionally evaluate associations between depression (PROMIS-D), anxiety (PROMIS-A), sleep (PROMIS-Sleep Disturbance), menopausal status, fatigue (FACIT-F), estimated pre-cancer IQ (WTAR), and cognitive effort (NASA-TLX) with both objective (DMS, HVLT-R, COWA, ANT, Digit Span) and self-reported (PROMIS) measures of cognitive function at baseline and post-chemotherapy. Linear mixed effects models will evaluate associations across pre- and post- time points.

Linear regression modeling will describe the associations between pre- to post-chemotherapy cognitive changes (DMS, HVLT-R, COWA, ANT, Digit Span, PROMIS) with post-chemotherapy depression and anxiety (PROMIS), HRQOL (FACT-G), and performance status (KPS).

Descriptive statistics will be used to estimate feasibility: 1.) recruitment rate (% of invited participants who enroll), 2.) attrition (% of enrolled participants who are not eligible for analysis of the primary outcome), and 3.) adherence to treatment (% self-reported doses of memantine taken).

We will tabulate all AEs, the dose at which they occurred, and if they led to dosing delays or removal from the study.

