### Appendix E: Trail Making Test (TMT)

#### Test Part A:

**Test Part B:**

## Appendix F: Patient Reported Outcomes Measurement Information System – Modified Cognitive Function

Please respond to each question or statement by marking one box per row.

[figure not shown]
In the past 7 days...

|   |  | Never | Rarely
(Once) | Sometimes
(Two or
three times) | Often
(About
once a day) | Very often
(Several
times a
day) |
|---|--|-------|------------------|--------------------------------------|--------------------------------|---|
| 1 | My thinking has been slow.....   | 5     | 4                | 3                                    | 2                              | 1   |
| 2 | It has seemed like my brain
was not working as well as
usual.....  | 5     | 4                | 3                                    | 2                              | 1   |
| 3 | I have had to work harder than
usual to keep track of what I
was doing.....  | 5     | 4                | 3                                    | 2                              | 1   |
| 4 | I have had trouble shifting back
and forth between different
activities that require thinking....  | 5     | 4                | 3                                    | 2                              | 1   |
| 5 | I have had trouble
concentrating .....  | 5     | 4                | 3                                    | 2                              | 1   |
| 6 | I have had to work really hard
to pay attention or I would
make a mistake .....  | 5     | 4                | 3                                    | 2                              | 1   |
| 7 | I have had trouble forming
thoughts .....   | 5     | 4                | 3                                    | 2                              | 1   |
| 8 | I have had trouble adding or
subtracting numbers in my
head.....   | 5     | 4                | 3                                    | 2                              | 1   |
| 9 | I have had trouble
remembering whether I did
things I was supposed to do,
like taking a medicine or
buying something I needed..... | 5     | 4                | 3                                    | 2                              | 1   |

**Before my cancer diagnosis...**

|    |   | Never | Rarely
(Once)                      | Sometimes
(Two or
three times) | Often
(About
once a day)   | Very often
(Several
times a
day) |

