## Appendix K: PROMIS-Sleep Disturbance

Please respond to each question or statement by marking one box per row.

**In the past 7 days...**

|   |                           | Very poor | Poor | Fair | Good | Very good |
|---|---------------------------|-----------|------|------|------|-----------|
| 1 | My sleep quality was..... | 5         | 4    | 3    | 2    | 1         |

**In the past 7 days...**

|   |   | Not at all | A little bit | Somewhat | Quite a bit | Very much |
|---|---|------------|--------------|----------|-------------|-----------|
| 2 | My sleep was refreshing .....                       | 5          | 4            | 3        | 2           | 1         |
| 3 | I had a problem with my sleep ....                  | 1          | 2            | 3        | 4           | 5         |
| 4 | I had difficulty falling asleep .....               | 1          | 2            | 3        | 4           | 5         |
| 5 | My sleep was restless.....                          | 1          | 2            | 3        | 4           | 5         |
| 6 | I tried hard to get to sleep.....                   | 1          | 2            | 3        | 4           | 5         |
| 7 | I worried about not being able to fall asleep ..... | 1          | 2            | 3        | 4           | 5         |
| 8 | I was satisfied with my sleep .....                 | 5          | 4            | 3        | 2           | 1         |

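### The direction stated for the PROMIS Cognitive Function score in section 5.8.10 is the reverse of the item coding in Appendix F, so worsening self-reported cognition could be reported as improvement

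*Combined protocol and SAP*

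**What the plan says.** Section 5.8.10 adopts the eight-item PROMIS Cognitive Function short form, reported as a T-score (mean 50, SD 10). It adds one memory item and three items on self-perceived ability before cancer. It says that higher scores represent "greater degrees of cognitive complaints", so a high score is a bad one.

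Appendix F prints the form. Items 1 to 8 all describe problems, beginning with "My thinking has been slow". Each is coded Never = 5, Rarely = 4, Sometimes = 3, Often = 2, Very often = 1. The added memory item (item 9) is coded the same way.

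The measure is used in three places:

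- Secondary endpoint 3.2.1: changes in "self-reported (PROMIS Cognitive Function) cognitive measures will be measured from pre- to post-chemotherapy".
- Exploratory endpoint 3.3.1, in the volunteer subset: "PROMIS Cognitive function will be measured from pre- to 6 months post-chemotherapy".
- Section 9.3: paired t-tests on the changes, and regressions for "self-reported (PROMIS) measures of cognitive function at baseline and post-chemotherapy". Further regressions relate the pre-to-post change to post-chemotherapy depression, anxiety, FACT-G and KPS.

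Neither 5.8.10, Appendix F nor 9.3 gives a reverse-coding rule, a conversion table, or the sign of change that counts as decline.

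**The concern.** The two descriptions of the same score point in opposite directions. An analyst who sums the codes as printed and then interprets the result by 5.8.10 will call a decline an improvement, and an improvement a decline.

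This is the trial's only self-reported cognition endpoint. The error would reach the pre-to-post result, the 6-month result, and the section 9.3 associations with depression, anxiety, sleep, menopausal status, fatigue, estimated IQ and cognitive effort. It would also reach the associations of change in self-reported cognition with later mood, quality of life and performance status.

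Section 1.5 says the study should help clarify how self-reported and objectively measured cognition relate, and the answer to that question depends on the sign. Section 9.3 lists PROMIS beside DMS, on which a higher score is better, without saying whether the two run the same way. With a single arm, no concurrent group is available whose course might expose a reversal.

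**Working it through.** The plan gives no figure to reproduce here. The check is of direction, followed by simple arithmetic.

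**Inputs.** Item codes come from Appendix F, items 1 to 8. The stated direction comes from 5.8.10.

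**Form sum.** Let S be the sum of the eight codes as printed.

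- No complaints (all Never): S = 8 × 5 = 40.
- Constant complaints (all Very often): S = 8 × 1 = 8.

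S therefore falls as complaints rise. A score that runs as 5.8.10 states needs each code replaced by 6 minus the code: R = 8 × 6 − S = 48 − S. It follows that change in R = −(change in S).

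**Worsening patients, same answer on every item:**

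| Pre to post | S as printed | Change in S | R reversed | Change in R |
|---|---|---|---|---|
| Rarely to Sometimes | 32 to 24 | −8 | 16 to 24 | +8 |
| Rarely to Often | 32 to 16 | −16 | 16 to 32 | +16 |
| Never to Very often | 40 to 8 | −32 | 8 to 40 | +32 |

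All three patients got worse. Appendix F coding shows a fall in each case, and 5.8.10 reads a fall as fewer complaints.

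**Effect on the analyses.** Since R is 48 minus S, replacing one by the other negates the mean change, the paired t statistic and every regression slope. The standard deviation of change, the absolute t and the two-sided p-value stay the same. Section 9.3 does not say whether the secondary tests are one- or two-sided. If a one-sided test in the direction of benefit were used, the reversal would turn p into 1 − p.

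**Comparison with the other PROMIS forms:**

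| Measure | Direction stated in the text | Direction of the printed codes | Agree? |
|---|---|---|---|
| Depression (5.8.12, Appendix I) | Higher is worse | Problem items, 1 to 5 | Yes |
| Anxiety (5.8.13, Appendix J) | Higher is worse | Problem items, 1 to 5 | Yes |
| Sleep Disturbance (5.8.14, Appendix K) | Higher is worse | Positive items 5 to 1, problem items 1 to 5 | Yes |
| Cognitive Function (5.8.10, Appendix F) | Higher is worse | Problem items, 5 to 1 | **No** |

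The sleep form is the most informative. Section 5.8.14 says "Higher scores represent greater sleep difficulties", and Appendix K prints its positive items already reversed: "My sleep was refreshing" is coded 5 for Not at all and 1 for Very much. The codes printed on that form are scoring codes. Read the same way, Appendix F yields a function score, on which high is good.

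**The case against.** The strongest reply is that the appendices are not scoring manuals. Section 5.8.15 says lower FACIT-F scores mean greater fatigue, yet Appendix L codes the item on feeling fatigued as 4 for Very much and gives no recoding step. FACT-G in Appendix N also mixes problem and positive items on one ascending 0 to 4 scale without a scoring rule. A missing reversal step is therefore common in this protocol and is weak evidence of an analysis error by itself.

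That stands as far as it goes, and it limits the comparison above to the PROMIS forms. It does not remove the conflict. FACIT-F and FACT-G put items of both directions on one response scale, so their printed codes plainly cannot be summed without recoding. The eight Appendix F items all run one way and can be summed as printed, with nothing to warn the analyst.

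Three other points are fair:

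- The reported score is a T-score, not a form sum, and an unstated inversion in the conversion could reconcile the two passages. None is described.
- Section 9.3 gives no direction of benefit for the other secondary measures either. This measure needs one more than they do, because its own description is contradictory.
- The item responses are collected in any case, so a wrong sign can be corrected at scoring.

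**Conclusion.** The concern holds. Section 5.8.10 and Appendix F give opposite directions for the same score, and nothing in the documents reconciles them.

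The consequence is one of sign only. It arises if scores built from the printed codes are interpreted by the 5.8.10 sentence, and it assumes that the T-score increases with the form sum. Under those conditions the self-reported cognition results for 3.2.1 and 3.3.1, and the related associations in 9.3, would all be read backwards. The primary DMS endpoint, sample size, feasibility and safety are untouched. This should be fixed before the secondary analyses are run, but it does not threaten the main conclusion of the trial.

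**What to change.** Replace the sentence in 5.8.10 with one that matches Appendix F, for instance: *A higher score means better self-reported cognitive function, that is, fewer complaints.* If the opposite direction is really wanted, keep the sentence and add an explicit step that replaces each item code with 6 minus the code before scoring.

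In either case, state in 9.3 which sign of change in this measure means decline, and check the scoring code against that statement. A test record that worsens from Rarely to Sometimes on all eight items is enough to confirm the direction.

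The cost is one sentence in 5.8.10, one phrase in 9.3 and a short code check. Data collection does not change.
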